#### 18.3. Risks Associated with the Study Device(s)

There are no additional known risks associated with the investigational device in comparison to commercially-available devices.

## 18.4. Risks associated with Participation in the Clinical Study

The following risks maybe associated with subjects' participation in the clinical study:

- Subjects may find it difficult, uncomfortable, or tiresome to complete study visits and/or questionnaires, including discomfort during 'meds off' or 'meds on' conditions for testing;
- Subjects with postural instability or gait disturbances either due to Parkinson's
  disease or as a side effect of DBS may be at a risk of falling while walking, rising
  from a chair, or sitting down in a chair as required for certain study assessments.

#### 18.5. Possible Interactions with Concomitant Medical Treatments

While concomitant use of anti-Parkinson medications is being adjusted to fit the subject's changed requirements with use of DBS, subjects may experience symptoms of excess or inadequate dopaminergic states (beyond those occurring due to Parkinson's disease). These may include increased dyskinesias, apathy, or other risks already listed in the sections above.

#### 18.6. Risk Minimization Actions

Additional risks may exist. Risks can be minimized through compliance with this protocol, performing procedures in the appropriate hospital environment, adherence to subject selection criteria, close monitoring of the subject's physiologic status during research procedures and/or follow-ups and by promptly supplying BSC with all pertinent information required by this protocol.

#### 18.7. Anticipated Benefits

High frequency stimulation of deep brain structures has been used since the 1980s for the treatment of motor symptoms associated with PD. Many studies have measured the risks and benefits associated with this type of treatment, and considerable reduction in PD symptoms has been observed. It is possible that some individual patients may experience no direct benefit from participation in this study. However, based on the success of the Boston Scientific VerciseTM DBS Systems, it is anticipated that most patients will experience improvement in PD symptoms. The programming options with the VerciseTM CartesiaTM 16-contact Directional Leads to potentially improve therapy and/or reduce stimulation-related side effects are anticipated to be perceived as benefits.

#### 18.8. Risk to Benefit Rationale

The purpose of this study is to document patient outcomes including effectiveness for the BSC Vercise™ DBS Systems including the Vercise™ Cartesia™ 16-contact Directional Leads for the treatment of PD. Based on the clinical data for the approved Vercise™ DBS

Systems, the risk-to-benefit ratio for use of the Vercise™ DBS Systems with the Vercise™ Cartesia™ 16-contact Directional Leads is within reason for foreseeable risks. However, studies do not always predict all side effects that may be experienced. Observation and follow-up of all patients is required as outlined in the protocol.

The components used in this study are similar to others in the Vercise™ DBS Systems and other commercial DBS devices that have an extensive history of use in the treatment of PD. Based on clinical experience with the therapy, the anticipated risks associated with the use of the study device are predicted to be acceptable compared to the expected benefits in the reduction of PD symptoms. The treatment is reversible in that the device may be turned off or explanted at any time for any reason.

All efforts will be made to minimize the aforementioned potential risks using the following approaches:

- Selection of Investigators (neurologists and neurosurgeons) who are experienced and skilled in the treatment of patients with Parkinson's Disease as per BSC's site selection and qualification procedures;
- Clearly defined inclusion and exclusion criteria that ensure only appropriate patients are enrolled;
- Ensuring that treatment and follow-up of patients is consistent with current medical practice;
- Safety review processes by Boston Scientific;
- Monitoring visits to investigational sites.

# 19. Safety Reporting

# 19.1. Reportable Events by investigational site to Boston Scientific

It is the responsibility of the investigator to assess and report to BSC any event which occurs in any of following categories:

- Non-related Adverse Events that occur within 1-year post activation
- All Procedure Related Adverse Events
- All Device Hardware and/or Stimulation Related Adverse Events
- All Serious Adverse Events (regardless of relationship)
- All Device Deficiencies
- Unanticipated Serious Adverse Device Effects (USADE)

New findings/updates in relation to already reported events

When possible, the medical diagnosis should be reported as the Event Term instead of individual symptoms.

If it is unclear whether or not an event fits one of the above categories, or if the event cannot be isolated from the device or procedure, it should be submitted as an adverse event and/or device deficiency.

Any reportable event required by the protocol, experienced by the study subject after informed consent and once considered enrolled in the study (as defined in study subject classification section), whether prior to, during or subsequent to the study procedure, must be recorded in the eCRF.

Underlying diseases and chronic conditions are not reported as AEs unless there is an increase in severity or frequency during the course of the investigation. Death should not be recorded as an AE, but should only be reflected as an outcome of one (1) specific SAE (see Table 19.2-1 for AE definitions).

Refer to Section 18 for the known risks associated with the study device(s).

# 19.2. Definitions and Classification

Adverse event definitions are provided in Table 19.2-1. Administrative edits were made on the safety definitions from 21 CFR Part 812, ISO 14155 and EU MDR 2017/745/MDCG 2020-10/-1 Guidance on Safety Reporting in Clinical Investigations for clarification purposes.

Table 19.2-1: Safety Definitions

Term	Definition	
Adverse Event (AE)	Any untoward medical occurrence, unintended disease or injury, or any untoward clinical signs (including an abnormal laboratory finding) in subjects, users or other persons, in the context of a clinical investigation whether or not related to the investigational medical device and whether or	
Ref: ISO 14155		
Ref: MDCG 2020-10/1	not anticipated or unanticipated.	
	NOTE 1: This includes events related to the investigational medical device or comparator.	
	NOTE 2: This definition includes events related to the procedures involved.	
	NOTE 3: For users or other persons, this definition is restricted to events related to the investigational medical device.	
Adverse Device Effect (ADE)	Adverse event related to the use of an investigational medical device	
Ref: ISO 14155	NOTE 1: This includes any adverse event resulting from insufficiencies or inadequacies in the instructions for use, the deployment, the	
Ref: MDCG 2020-10/1		

Table 19.2-1: Safety Definitions

Term	Definition	
	implantation, the installation, the operation, or any malfunction of the investigational medical device.	
	NOTE 2: This definition includes any event resulting from use error or from unintentional misuse of the investigational medical device.	
	NOTE 3: This includes 'comparator' if the comparator is a medical device.	
Serious Adverse Event (SAE)	Adverse event that led to any of the following: a) death,	
Ref: ISO 14155	b) serious deterioration in the health of the subject, user or other persons	
Ref: MDCG 2020-10/1	as defined by either:  1) a life-threatening illness or injury, or	
	
 
a permanent impairment of a body structure or a body function, including chronic diseases or
 
	
	
 
in-patient hospitalization or prolongation of existing hospitalization, or
 
	
	medical or surgical intervention to prevent life-threatening illness or injury or permanent impairment to a body structure or a body function	
	
 
c) foetal distress, foetal death, or a congenital abnormality or birth defect including physical and mental impairment.
 
	
	NOTE 1: Planned hospitalization for a pre-existing condition, or a procedure required by the clinical investigational plan, without a serious deterioration in health, is not considered a serious adverse event.	
Serious Adverse Device Effect (SADE)	Adverse device effect that has resulted in any of the consequences characteristic of a serious adverse event.	
Ref: ISO 14155		
Ref: MDCG 2020-10/1		
Unanticipated Adverse Device Effect (UADE)  Ref: 21 CFR Part 812	Any serious adverse effect on health or safety or any life-threatening problem or death caused by, or associated with, a device, if that effect, problem, or death was not previously identified in nature, severity, or degree of incidence in the investigational plan or application (including a supplementary plan or application), or any other unanticipated serious	
	problem associated with a device that relates to the rights, safety, or welfare of subjects.	
Unanticipated Serious Adverse Device Effect (USADE)	Serious adverse device effect which by its nature, incidence, severity, or outcome has not been identified in the current risk assessment.	
Ref: ISO 14155	NOTE 1: Anticipated serious adverse device effect (ASADE) is an effect which by its nature, incidence, severity or outcome has been identified in	
Ref: MDCG 2020-10/1	the risk assessment.	

Table 19.2-1: Safety Definitions

Term	Definition	
Serious Health Threat	Signal from any adverse event or device deficiency that indicates an imminent risk of death or a serious deterioration in the health in subjects, users or other persons, and that requires prompt remedial action for other subjects, users or other persons.  Note 1 to entry: This would include events that are of significant and unexpected nature such that they become alarming as a potential serious health hazard or possibility of multiple deaths occurring at short intervals.	
Ref: ISO 14155		
Device Deficiency	An inadequacy of a medical device related to its identity, quality, durability, reliability, usability, safety or performance.	
Ref: ISO 14155		
Ref: MDCG 2020-10/1	NOTE 1: Device deficiencies include malfunctions, use errors, and inadequacy in the information supplied by the manufacturer including labeling.	
	NOTE 2: This definition includes device deficiencies related to the investigational medical device or the comparator.	

The following definitions will be used for defining hospitalization or prolongation of hospitalization for SAE classification purposes:

classification purposes:		
Hospitalizations	Hospitalization does not include:	
	
 
emergency room visit that does not result in in-patient admission
 
	
	Note: although an emergency room visit does not itself meet the definition for hospitalization, it may meet other serious criteria (e.g. medical or surgical intervention to prevent permanent impairment or damage)	
	
 
elective and pre-planned treatment/surgery for a pre-existing condition that is documented in the subject's record at the time of consent/enrollment
 
admission for social reasons and/or respite care in the absence of
 
	
	any deterioration in the subject's general condition (e.g. subject is homeless, caregiver relief)	
	
 
pre-planned, protocol-specified admission related to the clinical study (e.g. procedure required by protocol)
 
	
Prolongation of hospitalization	In-patient admission to the hospital that is prolonged beyond the expected standard duration for the condition under treatment.	
	Note: new adverse events occurring during the hospitalization are evaluated to determine if they prolonged hospitalization or meet another SAE criteria.	

# 19.3. Relationship to Study Device(s) (Investigational Device(s))

The Investigator must assess the relationship of the reportable AE to the study device hardware, device stimulation and/or study procedure. See criteria in Table 19.3-1:

Table 19.3-1: Criteria for Assessing Relationship of Study Device (Investigational Device(s)) or Procedure to Adverse Event

Classification	Description	
Not Related	Relationship to the device, comparator or procedures can be excluded when:	
Ref: MDCG 2020- 10/1	- the event has no temporal relationship with the use of the investigational device or the procedures related to the use of the investigational device;	
	
 
the serious event does not follow a known response pattern to the medical device (if the response pattern is previously known) and is biologically implausible;
 
	
	
 
the discontinuation of medical device application or the reduction of the level of activation/exposure - when clinically feasible – and reintroduction of its use (or increase of the level of activation/exposure), do not impact on the serious event;
 
	
	
 
the event involves a body-site or an organ that cannot be affected by the device or procedure;
 
	
	
 
the serious event can be attributed to another cause (e.g. an underlying or concurrent illness/ clinical condition, an effect of another device, drug, treatment or other risk factors);
 
	
	
 
the event does not depend on a false result given by the investigational device used for diagnosis, when applicable;
 
	
	In order to establish the non-relatedness, not all the criteria listed above might be met at the same time, depending on the type of device/procedures and the serious event.	
Possibly Related Ref: MDCG 2020- 10/1	The relationship with the use of the investigational device or comparator, or the relationship with procedures is weak but cannot be ruled out completely. Alternative causes are also possible (e.g. an underlying or concurrent illness/clinical condition or/and an effect of another device, drug or treatment). Cases where relatedness cannot be assessed or no information has been obtained should also be classified as possible.	
Probably Related Ref: MDCG 2020- 10/1	The relationship with the use of the investigational device or comparator, or the relationship with procedures seems relevant and/or the event cannot be reasonably explained by another cause, but additional information may be obtained.	

Table 19.3-1: Criteria for Assessing Relationship of Study Device (Investigational Device(s)) or Procedure to Adverse Event

Classification	Description	
Causal Relationship  Ref: MDCG 2020-	The serious event is associated with the investigational device or comparator or with procedures beyond reasonable doubt when:	
10/1	
 
the event is a known side effect of the product category the device belongs to or of similar devices and procedures;
 
	
	
 
the event has a temporal relationship with investigational device use/application or procedures;
 
	
	- the event involves a body-site or organ that	
	-the investigational device or procedures are applied to;	
	
 
-the investigational device or procedures have an effect on;
 
	
	
 
the serious event follows a known response pattern to the medical device (if the response pattern is previously known);
 
	
	- the discontinuation of medical device application (or reduction of the level of activation/exposure) and reintroduction of its use (or increase of the level of activation/exposure), impact on the serious event (when clinically feasible);	
	
 
other possible causes (e.g. an underlying or concurrent illness/ clinical condition or/and an effect of another device, drug or treatment) have been adequately ruled out;
 
	
	- harm to the subject is due to error in use;	
	- the event depends on a false result given by the investigational device used for diagnosis, when applicable;	
	In order to establish the relatedness, not all the criteria listed above might be met at the same time, depending on the type of device/procedures and the serious event.	

## 19.4. Investigator Reporting Requirements

The communication requirements for reporting to BSC are as shown in Table 19.4-1.

The investigator must report all non-related Adverse Events up to Year 1 Post Activation.

The investigator must report all Adverse Device Effects, Serious Adverse Events (regardless of relationship to device (hardware or stimulation) and/or procedure), Unanticipated Serious Adverse Device Effects, and Device Deficiencies for each subject from the time of Informed Consent through the end of study participation.

These events may be reported via phone, fax or email if the electronic data capture (EDC) system is unavailable. The paper AE Notification Form or Device Deficiency Notification Form should be used to report AEs and/or device deficiencies during this time.

Table 19.4-1: Investigator Reporting Requirements

Event Classification	Communication Method	Communication Timeline pre-market studies (21 CFR Part 812, /MDCG 2020-10/1)
Unanticipated Serious Adverse Device Effect	Complete AE eCRF page with all available new and updated information.	Within 1 business day of first becoming aware of the event.      Terminating at the end of the study
	Provide all relevant source documentation (de- identified/ pseudonymized) for reported event.	Immediately, when documentation is available
Serious Adverse Event	Complete AE eCRF page with all available new and updated information.	Immediately but not later than 3 calendar days of first becoming aware of the event or as per local/regional regulations.  Reporting required through the end of the study
	Provide all relevant source documentation (de- identified/ pseudonymized) for reported event.	At request of sponsor
Serious Adverse Device Effects	Complete AE eCRF page with all available new and updated information.	Immediately but not later than 3 calendar days of first becoming aware of the event or as per local/regional regulations.
		
 
Reporting required through the end of the study
 

	Provide all relevant source documentation (de-	
 
Immediately, when documentation is available
 

	identified/ pseudonymized) for reported event.	At request of sponsor
Device Deficiencies (including but not limited to malfunctions, use errors and inadequacy in information supplied by the manufacturer, including labeling)	Complete device deficiency eCRF with all available new and updated information.	Immediately but not later than 3 calendar days of first becoming aware of the event.      Reporting required through the end of the study
Note: Any Device Deficiency that might have led to a serious adverse event if appropriate action had not been taken, intervention had not occurred, circumstances had been less fortunate is considered a reportable event.	Provide all relevant source documentation (de- identified/ pseudonymized) for reported event.	At request of sponsor

Table 19.4-1:	Investigator	Reporting	Requirements
---------------	--------------	-----------	--------------

Event Classification	Communication Method	Communication Timeline pre-market studies (21 CFR Part 812, /MDCG 2020-10/1)
Adverse Event including Adverse Device Effects	Complete AE eCRF page, which contains such information as date of AE, treatment of AE resolution, assessment of seriousness and relationship to the device.  Provide all relevant source documentation (deidentified/pseudonymized) for reported event.	
 
In a timely manner (e.g. Recommend within 10 business days) after becoming aware of the information
 
All non related, non- serious adverse events reporting are required through 1 year post activation
 
All related adverse events (ADEs) are required through end of the study.
 
At sponsor request
 

\* Please note that pre-market studies are clinical studies with investigational devices or with medical devices that bear the regulatory approval and are not being used for the same approved indications.

# NOTES:

- Sensations or side effects that occur during programming should not be reported as AEs.
   However, persistent unpleasant sensations or side effects that occur after the completion of programming will be reported.
- Ineffective therapy (e.g. lack of efficacy, lack or decrease of therapeutic response) will not
  be collected as an adverse event, since failure to achieve therapeutic response is an issue of
  efficacy, not safety. No AE of "Ineffective Therapy" should be reported when using the
  expanded parameter range for purposes of improving ineffective therapy. However, AEs
  due to sudden loss of efficacy (e.g. loss of stimulation leading to a fall or injury) will be
  collected.
- The subject's Parkinson's disease symptoms will not be collected as AEs, unless they have
  worsened beyond baseline and beyond the expected disease progression over time. This
  worsening event could occur in the context of a device malfunction or with a properlyfunctioning device as determined by investigator).
- Device migration will not be collected as an adverse event. However, an AE that results from the device/lead migration should be reported as an AE. Device migration should be reported as a device deficiency in the electronic database.

In the case of death linked to device hardware or stimulation and/or procedure, autopsy and explantation of device is recommended. Every effort should be made to return the device to BSC. A copy of the death records including autopsy report should be sent to BSC per the Investigator Reporting Requirements (Table 19.4-1). The stimulator should be explanted in the case of cremation and returned to BSC. Cremation may cause the stimulator battery to explode.

Table 19.4-1: Investigator Reporting Requirements

Event Classification	Communication Method	Communication Timeline pre-market studies
		(21 CFR Part 812, /MDCG 2020-10/1)

For Germany, please also refer to the 'Serious Adverse Event Reporting according to MPKPV §3 (4) No. 7 & § 2 (1, 5) and §3 (4), (5), (7) & §5 (2) MPSV statement'.

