## 5. Device Description

Boston Scientific DBS Systems are comprised of leads for stimulation and extensions that allow the leads to be extended to reach the Implantable Pulse Generator (IPG). The various components are shown in Error! Not a valid bookmark self-reference..

The Boston Scientific Vercise™ Cartesia™ X/HX 16-contact Directional Leads (30 cm or 45 cm) used with a commercially approved Vercise™ Genus 32-contact IPG will provide directional stimulation. These leads extend the span of contacts when compared with commercially available directional leads. However, the length of the distal contact array span is no greater than that of the existing standard DBS 8-contact Leads with non-directional arrays.

Once the leads are placed, they are typically secured using standard lead fixation technique. A commercially available SureTekTM Burr Hole Cover may be used. Since the leads are often placed under the scalp for some time before being connected to lead extensions or IPG, lead boots may be used to cover the proximal ends of the leads during this period. External commercially available devices, including a Clinician Programmer, Remote Control and Charging System, are provided for patient/physician use. Boston Scientific's GUIDE XT software may be used as a planning tool for programming as applicable.

The leads, lead extensions, and OR cable will be considered test devices in the study. All other components of the DBS system are commercially approved.

[figure not shown]

Figure 1: Cartesia X/HX 16-contact Directional Lead with Genus DBS System

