# 10.11. Replacements/Revisions

It is possible that leads may be placed incorrectly, migrate, fail or get infected. This may require repositioning, replacement or explant. It is also possible that the IPG may fail and require replacement or explant, or need repositioning due to migration, discomfort, etc. The decision to reposition or replace any device component will be made by the investigator along with the subject. Site staff should notify BSC before the procedure. Subjects not agreeing to a recommended lead revision will be withdrawn from the study but will be included in the intent-to-treat and safety analyses. Subjects agreeing to lead revision will continue on study and will be followed according to the study schedule. Effectiveness data from these subjects will be included in the intent-to-treat analysis. Any replacements, revisions or explants performed during the course of the study should be recorded in the electronic database. Subjects who are not willing to an IPG revision will only be withdrawn, per investigator discretion, if the performance of the device has been compromised e.g. unable to charge due to migration.

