#### 19.5. Boston Scientific Device Deficiencies

Device deficiencies for Boston Scientific devices will be documented and reported to BSC. If possible, the investigational device(s) should be returned to BSC for analysis. Instructions for returning the investigational device(s) will be provided. Device deficiencies should also be documented in the subject's source records.

Device deficiencies are not adverse events. However, an adverse event that results from a device deficiency would be recorded as an adverse event on the appropriate eCRF.

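### Does filing lead migration as a device deficiency, although Section 18 lists it as an anticipated adverse event, leave a hole in the lead-safety data?

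*Combined protocol and SAP*

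**What the plan says.** Section 5 makes the lead part of what is under test: "The leads, lead extensions, and OR cable will be considered test devices in the study". Section 18.1 lists migration of the lead, extension or IPG, and loss of adequate stimulation, among the anticipated adverse events. Section 18.2 repeats both as anticipated adverse device effects. Section 18.1 also expects the kind and frequency of lead-related adverse events to resemble those of marketed leads.

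The notes to Section 19.4 set the collection rule in three sentences. The first is "Device migration will not be collected as an adverse event". The second is "However, an AE that results from the device/lead migration should be reported as an AE". The third is "Device migration should be reported as a device deficiency in the electronic database". On loss of benefit, the same notes say "Ineffective therapy (e.g. lack of efficacy, lack or decrease of therapeutic response) will not" count as an adverse event. Section 19.5 gives the general rule: "Device deficiencies are not adverse events. However, an adverse event that results from a device deficiency would be recorded as an adverse event".

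Table 19.4-1 sets the deadline for device deficiencies as "Immediately but not later than 3 calendar days of first becoming aware of the event", with reporting through the end of the study. Section 10.11 adds: "Any replacements, revisions or explants performed during the course of the study should be recorded in the electronic database".

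**The concern.** The same event appears under adverse event headings in Section 18 and is barred from adverse event collection in Section 19.4. The definitions in Section 19.2 make this look more serious. An adverse device effect is a kind of adverse event, a serious adverse device effect is a kind of adverse device effect, and an unanticipated one is a kind of serious one. Hospitalization and surgical intervention make an event serious only if it is an adverse event to begin with. An event kept out at the first step cannot enter any later category.

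Suppose a test lead migrates, the patient loses benefit but is no worse than at baseline, and the lead is repositioned without complication. Under these rules no adverse event record is required, although the patient has had a second operation because of the device under study. A lead-safety rate counted from adverse events would omit that patient, and the omission always favours the device. If such a rate were set against a rate for marketed leads that did count migration and revision, the comparison would not be like with like.

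**Working it through.** The plan states no lead-safety figure to reproduce, so the check consists of following the event through the rules and asking what is recorded, what is lost, and which stated result would change.

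1. **The migration itself.** Section 19.4 names it, excludes it from adverse events and assigns it to device deficiencies. Device deficiencies are reportable under Section 19.1 and are due within 3 calendar days until the study ends. *Recorded.*

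2. **Harm caused by the migration.** Sections 19.4 and 19.5 both send it to the adverse event record. *Recorded.*

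3. **Loss of benefit.** Reduced response alone is not an adverse event. The Section 19.4 notes do collect Parkinson's symptoms that worsen past baseline and past expected progression, with device malfunction given as one possible setting. They also collect adverse events due to a sudden loss of efficacy. *Recorded as an adverse event unless the loss is without injury and the patient is no worse than baseline and expected progression.*

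4. **The revision.** Section 10.11 requires it to be recorded. Complications of the surgery are procedure-related adverse events, which Section 19.1 makes reportable. *Recorded.*

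5. **What is left.** Only migration with loss of benefit that stays within the limits in step 3, followed by an uncomplicated revision, yields no required adverse event. Even then there is a device-deficiency record and a revision record. The gap is in the label, not in the capture.

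6. **Do Sections 18 and 19 conflict as rules?** Section 18 is headed as potential risks and benefits, and Section 19.1 points back to it for the device's known risks. Its contents fit that role: it includes radiation exposure from imaging, electromagnetic interference and poor initial lead position. It also names death, which Section 19.1 says is entered as the outcome of a serious adverse event and not as an adverse event itself. The list therefore cannot be a coding instruction. Section 19.4 is the section that gives one.

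7. **Could sites code migration differently?** Section 19.1 allows an event to be submitted as an adverse event, a device deficiency or both when its category is unclear or it cannot be separated from the device or procedure. Migration as such is not unclear, because Section 19.4 settles it by name.

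8. **Which analysis would be biased?** Sections 6.1 and 11.1 define an effectiveness endpoint, the change in MDS-UPDRS III. Section 6 says only that safety data are collected as well. The sentence in Section 18.1 about similar lead-related events is part of the risk rationale. It carries no hypothesis, threshold or planned comparison. Section 11.2.4 leaves further analysis detail to the SAP, and parts of the statistical text cannot be read here, so a table of deficiencies and revisions may already be specified.

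9. **Size.** An undercount would need a migration rate, a share of migrations following the path in step 5, and a safety denominator. The documents show none of these. Each such patient would lower an adverse-event-only count by one, but that holds for any uncounted event and does not measure an effect.

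**The case for a change.** The strongest case for a change is that capture does not guarantee reporting. The lead is the device under test, migration is a plausible way for it to fail, and the protocol words its own safety expectation in terms of adverse events. An adverse-event-only table would be incomplete for that expectation, in the direction that favours the sponsor. The mismatch also reaches beyond migration. Section 18 lists component failure or malfunction, with or without explant, as an anticipated adverse event, while Section 19.2 counts malfunctions as device deficiencies. A combined table would need no new data.

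Part of this stands. Sections 18 and 19 do use different labels for the same event, and Section 10.11 does not say whether an uncomplicated revision is itself an adverse event. A reader given only an adverse event table would see too little about the lead. Showing device deficiencies and revisions beside the adverse events is good practice, above all if any statement is made about marketed leads.

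The claim of a biased result does not stand, because no adverse-event-based lead rate or comparison is defined in the readable text. The malfunction example supports reading Section 18 as a risk list, since it shows the same pattern for a whole class of events. Keeping deficiencies apart from adverse events follows the protocol's own definitions.

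**Conclusion.** The concern does not call for a change. The difference between Section 18 and Sections 19.4 and 19.5 is one of wording: a list of risks uses adverse event headings for something that the reporting rule files elsewhere. On the one narrow path that gives no required adverse event, the migration and the revision are still recorded, and an analyst can tabulate them beside the adverse events without amending the plan. No stated result or conclusion changes, and the primary endpoint is unaffected.

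The size of any undercount in an adverse-event-only rate is unknown and cannot be derived from the documents; it is zero if no patient follows that path. The conclusion rests on two assumptions: that sites follow Section 19.4 for migration and Section 10.11 for revisions, and that the unreadable statistical text contains no formal lead-safety endpoint counted from adverse events alone. If such an endpoint exists, or a comparison with marketed leads is later reported, migration and revision would have to be counted the same way on both sides.
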